9.1 Scope/Schema

This section outlines all in-person visits study participants have with the study staff. All dates listed below are relative to the day of enrollment for each participant (**see Appendix E**).

Participants – Intervention Group

- Day 1 (Month 1, Week 1) = T0 (by convention we identify the baseline visit as “T0”)
 - Food bank client participates in diabetes screening (blood glucose and/or HbA1c testing) event at food pantry; study staff verifies that client meets eligibility requirements for study inclusion
 - Client agrees to participate in study and completes written consent form with study staff
 - Participant completes baseline survey with study staff (CASIC)
 - Participant randomly assigned to study intervention group by study staff

- Participant receives 1st bi-monthly food box and passive education materials and receives information from food bank staff on group diabetes education classes
- Month 1, Week 2
 - Participant receives bi-monthly food box, passive education materials, and 1-on-1 education from food bank staff
 - Participant attends Session 1 of group diabetes education class around this time
- Month 2, Week 1
 - Participant receives bi-monthly food box, passive education materials, and 1-on-1 education from food bank staff
 - Participant attends Session 2 of group diabetes education class around this time
- Month 2, Week 2
 - Participant receives bi-monthly food box, passive education materials, and 1-on-1 education from food bank staff
- Month 3, Week 1
 - Participant receives bi-monthly food box, passive education materials, and 1-on-1 education from food bank staff
 - Participant attends monthly group drop-in diabetes education class around this time
- Month 3, Week 2 = T3
 - Participant completes 3-month HbA1c test with study staff
 - Participant receives bi-monthly food box, passive education materials, and 1-on-1 education from food bank staff
- Month 4, Week 1
 - Participant receives bi-monthly food box, passive education materials, and 1-on-1 education from food bank staff
 - Participant attends monthly group drop-in diabetes education class around this time
- Month 4, Week 2
 - Participant receives bi-monthly food box, passive education materials, and 1-on-1 education from food bank staff
- Month 5, Week 1
 - Participant receives bi-monthly food box, passive education materials, and 1-on-1 education from food bank staff
 - Participant attends monthly group drop-in diabetes education class around this time
- Month 5, Week 2
 - Participant receives bi-monthly food box, passive education materials, and 1-on-1 education from food bank staff
- Month 6, Week 1 = T6
 - Participant completes 6-month HbA1c test with study staff
 - Participant completes T6 survey with study staff (CASIC)
 - Participant receives \$30 gift card for completion of survey
 - Participant receives final bi-monthly food box, passive education materials, and 1-on-1 education from food bank staff
 - Participant attends monthly group drop-in diabetes education class
- Month 12 = T12

- Participant completes 12-month HbA1c test with study staff
- Participant completes T12 INT survey with study staff (CASIC)
- Participant receives \$15 gift card for completion of survey
- Participant formally exits research study

Participants – Control Group

- Day 1 (Month 1, Week 1) = T0
 - Food bank client participates in diabetes screening (blood glucose and/or HbA1c testing) event at food pantry; study staff verifies that client meets eligibility requirements for study inclusion
 - Client agrees to participate in study and completes written consent form with study staff
 - Participant completes baseline survey with study staff (CASIC)
 - Participant randomly assigned to study control group by study staff
 - Participant receives \$15 gift card for survey completion
- Month 1, Week 1 – Month 6, Week 2
 - Participant attends regular food pantry distributions and receives normal services per food pantry guidelines (does NOT receive diabetes food packages or education)
- Month 7, Week 1 = T6
 - Participant completes HbA1c test with study staff
 - Participant completes final survey with study staff (CASIC)
 - Participant receives \$15 gift card for survey completion
 - Participant receives 1st bi-monthly food box, passive education materials, and 1-on-1 education from food bank staff
- Month 7, Week 2
 - Participant receives bi-monthly food box, passive education materials, and 1-on-1 education from food bank staff
- Month 8, Week 1
 - Participant receives bi-monthly food box, passive education materials, and 1-on-1 education from food bank staff
- Month 8, Week 2
 - Participant receives bi-monthly food box, passive education materials, and 1-on-1 education from food bank staff
- Month 9, Week 1
 - Participant receives bi-monthly food box, passive education materials, and 1-on-1 education from food bank staff
- Month 9, Week 2 = T9
 - Participant receives bi-monthly food box, passive education materials, and 1-on-1 education from food bank staff
 - Participant completes HbA1c test with study staff
- Month 10, Week 1
 - Participant receives bi-monthly food box, passive education materials, and 1-on-1 education from food bank staff
- Month 10, Week 2

- Participant receives bi-monthly food box, passive education materials, and 1-on-1 education from food bank staff
- Month 11, Week 1
 - Participant receives bi-monthly food box, passive education materials, and 1-on-1 education from food bank staff
- Month 11, Week 2
 - Participant receives bi-monthly food box, passive education materials, and 1-on-1 education from food bank staff
- Month 12, Week 1 = T12
 - Participant receives final bi-monthly food box, passive education materials, and 1-on-1 education
 - Participant completes T12 HbA1c test with study staff
 - Participant completes T12 CONT survey with study staff (CASIC)
 - Participant receives \$15 gift card for completion of survey
 - Participant formally exits research study

9.2 *Language capacity*

Informed consent, survey administration, and diabetes education must be provided to all Spanish-speaking participants by bilingual study staff. Other study contact may be conducted with an interpreter.

9.3 *Compensation*

In order to realistically compensate participants for the time they spend participating in this research study and encourage full participation, participants will be reimbursed according to the following schedule:

- Intervention Group: \$30 gift card on completion of T6 follow-up survey; \$15 gift card on completion of T12 follow-up survey
- Wait-List Control Group: \$15 gift card on completion of baseline survey; \$15 gift card on completion of T6 follow-up survey; \$15 gift card on completion of T12 follow-up survey

Compensation will be provided in the form of assorted store gift cards (e.g., Walmart, Target, etc., but **should not include major grocery stores**). Study staff will have participants sign the “Participant Compensation Receipt Form” (**Appendix AL**) upon receipt of a gift card.

9.3.1 *Transportation Vouchers*

If a study participant reports transportation costs as a major barrier to completing T6 and/or T12 follow-up activities, site staff can provide transportation vouchers (e.g., gas card, bus token, public transit pass, etc.) not to exceed \$10 in value. Transportation vouchers may be offered to study participants up to two times (at T6 and T12), and **only** for completing study follow-up activities. Transportation vouchers should not be used to assist participants in attending other study or

intervention activities, nor should they be used in place of existing participant compensation (see section 9.3 above).

Site staff should enter any information (date, amount, type, and notes) for participants who do receive transportation vouchers in the study MS Access database.

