3.3 Diabetes-appropriate food boxes

Through the 6-month intervention, FAITH-DM participants will receive 11 bi-monthly food packages (twice monthly). The main goal of the food packages will be to increase participants' access to foods appropriate for diabetes self-management. The food packages will aim to provide approximately 25% of a participant's food needs for the month, equating to about 11 meals from each food package. Additionally, the food packages will serve as a model for healthy food choices for people living with diabetes.

Food group servings for the baseline food package will include a box with non-perishable items (canned, boxed, or other shelf-stable vegetables, fruits, grains, meats, beans, etc.), as well as supplemental perishable items (e.g. fresh vegetables and fruits, bread, dairy, meat, poultry) in a bag intended to serve a household of 1-2 people. In order to address varying household sizes, guidelines for distribution of food packages will be as follows:

Household Size (# persons)	Food Package Guidelines
1 - 2	1 standard box of non-perishables and 1 standard bag of perishables
3 - 4	1 standard box of non-perishables and 2 standard bags of perishables
5 or more	2 standard boxes of non-perishables and 2 standard bags of perishables

Food Box Criteria:

Based on USDA guidelines for number of servings of different food groups for an adult male

- Sufficient food items and variety to create 11 meals
- Focus on vegetables and fruits, whole grains, low-fat dairy, lean meat
- Ideal breakdown of food package by servings
 - 30- 40% non-starchy vegetables
 - 10 - 20% fruit
 - 25% grains and other carbohydrates (includes corn and potatoes)
 - 25% lean protein and dairy

Food Group	What equals a choice?	Number of choices per food package

Vegetables - non-starchy vegetables including a variety of types. Canned should be low-sodium or “no salt added”.
	
Fresh vegetables: 1 head, 1 bunch or 1 pound = 1 choice Canned vegetables (no salt added), 15 oz = 1 choice Spaghetti sauce, 15 oz = 1 choice Frozen Vegetables, 16 oz = 1 choice
	
9 (Ideally 4-5 fresh/perishable and 4-5 shelf-stable)

Fruits - include a variety of fruits. Canned should be no-sugar added or packed in 100% juice. No fruit juice.
	
Fresh fruit: 1 bunch, 1 pound, or 4 pieces = 1 choice Frozen Fruit, 12 - 16 oz = 1 choice Canned Fruit, 15 oz = 1 choice
	
3 (Ideally 2 perishable and 1 shelf-stable)

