Month 5, Week 1	
 • Participant receives bi-monthly food box, passive education materials, and 1-on-1 education from food bank staff • Participant attends monthly group drop-in diabetes education class around this time
Month 5, Week 2	
 • Participant receives bi-monthly food box, passive education materials, and 1-on-1 education from food bank staff
T6: Month 6, Week 1	
 • Participant completes 6-month HbA1c test with study staff • Participant completes final survey with study staff • Participant receives \$30 gift card for completion of survey • Participant receives final bi-monthly food box, passive education materials, and 1-on-1 education from food bank staff • Participant attends monthly group drop-in diabetes education class • RA sends participant’s PCP the T6 provider communication packet and HCUS
T12: Month 12	
 • Participant completes 12-month HbA1c test with study staff

	
 • Participant completes T12 INT survey with study staff (CASIC) • Participant receives \$15 gift card for completion of survey • RA sends participant's PCP the T12 provider communication packet and HCUS • Participant formally exits research study
--	---

WAIT LIST CONTROL GROUP

TIMELINE	ACTIVITY / STUDY VISIT
T0: Day 1 (Month 1, Week 1)	
 • Food bank client participates in diabetes screening (blood glucose and HbA1c testing) event at food pantry; study staff verifies that client meets eligibility requirements for study inclusion • Client agrees to participate in study and completes written consent form with study staff (informed consent, HIPAA authorization, and medical records release form) • Participant completes baseline survey with study staff • Participant randomly assigned to study control group by study staff • Participant receives \$15 gift card for survey completion • RA sends participant's PCP the baseline provider communication packet (control)
Month 1, Week 1 – Month 6, Week 2	
 • Participant attends regular food pantry distributions and receives normal services per food pantry guidelines (does NOT receive diabetes food packages or education)

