T6: Month 7, Week 1	
 • Participant completes HbA1c test with study staff • Participant completes final survey with study staff • Participant receives \$15 gift card for survey completion • Participant receives 1st bi-monthly food box, passive education materials, and 1-on-1 education from food bank staff from food bank staff • RA sends participant's PCP the T6 provider communication packet and HCUS
Month 7, Week 2	
 • Participant receives bi-monthly food box, passive education materials, and 1-on-1 education from food bank staff
Month 8, Week 1	
 • Participant receives bi-monthly food box, passive education materials, and 1-on-1 education from food bank staff
Month 8, Week 2	
 • Participant receives bi-monthly food box, passive education materials, and 1-on-1 education from food bank staff
Month 9, Week 1	
 • Participant receives bi-monthly food box, passive education materials, and 1-on-1 education from food bank staff
T9: Month 9, Week 2	
 • Participant receives bi-monthly food box, passive education materials, and 1-on-1 education from food bank staff • Participant completes HbA1c test with study staff
Month 10, Week 1	
 • Participant receives bi-monthly food box, passive education materials, and 1-on-1 education from food bank staff
Month 10, Week 2	
 • Participant receives bi-monthly food box, passive education materials, and 1-on-1 education from food bank staff

Month 11, Week 1	
 Participant receives bi-monthly food box, passive education materials, and 1-on-1 education from food bank staff
Month 11, Week 2	
 Participant receives bi-monthly food box, passive education materials, and 1-on-1 education from food bank staff
T12: Month 12	
 Participant receives final bi-monthly food box, passive education materials, and 1-on-1 education from food bank staff Participant completes T12 HbA1c test with study staff Participant completes T12 CONT survey with study staff (CASIC) Participant receives \$15 gift card for completion of survey Participant formally exits research study

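### Section 9.1 and Appendix E place the T6 HbA1c about 30 days earlier for intervention than for control, although the test window and calendar give both arms one six-month target: a minor, avoidable timing risk

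*Combined protocol and SAP*

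**What the plan says.** Section 9.1 sets the time origin for its visit list: "All dates listed below are relative to the day of enrollment for each participant". The T6 visit, with HbA1c and survey, is then labelled "Month 6, Week 1 = T6" for intervention and "Month 7, Week 1 = T6" for control. Appendix E has the same pair, "T6: Month 6, Week 1" and "T6: Month 7, Week 1". The intervention entry nevertheless describes the test as a six-month one: "Participant completes 6-month HbA1c test with study staff". T12 does not differ in this way: it is in Month 12 in both arms (for control, "Month 12, Week 1 = T12").

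Other sections give a common target:

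- Sections 3.1.4 (HbA1c) and 7.6 (surveys) have identical T6 rows for the two arms, 5 to 7 months (6±1), with every month counted as 30 days.
- Section 3.6 treats T0 to T6 as a six-month period and keeps controls off the intervention until T6.
- Section 13.4.3 frames the primary hypothesis over six months.
- The Section 2.7 calendar starts both T6 columns in April 2016, six months after the first October 2015 enrollments, and ends both in March 2017.

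The primary model in Section 13.4.4 contains the treatment indicator and the baseline value of the outcome. It has no term for when the follow-up test was done.

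**The concern.** The T6 HbA1c carries the randomised comparison. Section 9 presents Appendix E as the schedule of what happens at each contact, so a site has reason to book visits from it. If it does, intervention participants are tested about a month earlier after enrollment than controls. Any HbA1c change over that month that has nothing to do with the programme would then enter the treatment estimate, and adjusting for baseline HbA1c would neither show it nor remove it.

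Existing checks would not catch the pattern. Both days are in window, so the out-of-window deviation code in Appendix F (code 13) is not triggered. No section plans to tabulate test day by arm.

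**Working it through.** **1. The plan's window in days.** From 3.1.4, with 30-day months: 5 × 30 = 150, 7 × 30 = 210, centre 6 × 30 = 180, for both arms.

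**2. The 9.1 labels in days.** Day 1 is Month 1, Week 1, and the list runs in two entries per month, matching the twice-monthly boxes. Reading labels as half-month slots: slot = 2 × (month − 1) + week; day from enrollment = 15 × (slot − 1).

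| Visit | Label | Slot | Day | Window (days) |
|---|---|---|---|---|
| Intervention T3 | Month 3, Week 2 | 6 | 75 | 60–120 |
| Intervention T6 | Month 6, Week 1 | 11 | 150 | 150–210 |
| Control T6 | Month 7, Week 1 | 13 | 180 | 150–210 |
| Control T9 | Month 9, Week 2 | 18 | 255 | 240–300 |
| Control T12 | Month 12, Week 1 | 23 | 330 | 330–390 |

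The T6 gap is 180 − 150 = 30 days, half of the 60-day window. Intervention sits on the lower edge and control at the centre. Reading the labels as calendar weeks, day = 30 × (month − 1) + 7 × (week − 1), gives 67, 150, 180, 247 and 330: the same gap, and every visit still in window.

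**3. What the 2.7 calendar implies.** Monthly recruits per food bank from October 2015 are 10, 20, 25, 25, 25, 20, 30, 30, and so on; half go to each arm.

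- Intervention caseload, March to May 2016, with exit after six months: 62.5; 77.5 − 5 = 72.5; 92.5 − 15 = 77.5. Printed: 63, 73, 78. Exit after five months would give 57.5, 62.5, 65.0.
- Controls receiving boxes (box column minus intervention column), April to August 2016: 78 − 73 = 5; 93 − 78 = 15; 109 − 81 = 28; 121 − 81 = 40; 131 − 78 = 53. A start at six months predicts 5, 15, 27.5, 40, 52.5; a start at five months predicts 15, 27.5, 40, 52.5, 62.5.

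Over these months the calendar was built on six months in both arms.

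**4. A likely origin of the difference.** Section 3.3 says "FAITH-DM participants will receive 11 bi-monthly food packages (twice monthly". Counting 11 slots from Day 1 puts the last intervention box at Month 6, Week 1. Controls wait through all 12 slots of Months 1 to 6 and take their first box at slot 13. Each arm's T6 test is listed with that box. The documents do not state this reason; it is an inference.

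**5. Scale only.** The plan's sample size reproduces: n = (1.960 + 1.282)² × (1.6² + 1.9²) × (1 − 0.51²) / 0.4² = 299.8, so 300 per arm. The planned standard error is √[(1.6² + 1.9²)(1 − 0.51²)/300] = 0.123 HbA1c points. If every visit fell on its nominal day, unrelated change over the 30 days would have to reach 0.04 points to move the estimate by 10% of the 0.4 target, or 0.123 points to move it by one standard error. If half the intervention tests were at day 150 and the rest at day 180, the mean gap would be 15 days and the required changes double to 0.08 and 0.247. These are thresholds, not estimates. Since HbA1c reflects about three months (3.1.4), tests 30 days apart share roughly 60 of 90 days.

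**The case against.** The rule that governs testing is already common to both arms. Section 3.1.4 states the window for HbA1c and 7.6 repeats it for surveys, while 9.1 is a schema whose two entries per month look like a box-distribution template. The other labels are loose as well: on the conversion above, T3 is at day 75, control T9 at day 255 and control T12 at day 330, each before its nominal month but in window. The 2.7 calendar, which sites also hold, plans both arms at six months, and its note on final intervention boxes falls in February 2017, six months after enrollment closes. The T12 footnote in 3.1.4 handles T6 completion at month 5 as a case needing accommodation, which would be odd if that were the routine intervention target.

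Most of this stands, and it makes the practical risk modest. It does not remove the conflict. Sites hold two schedules that disagree by arm on the primary outcome visit, and following either one leaves every visit in window and unlogged. The footnote also shows that T6 visits at month 5 were foreseen.

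A reader might go further and infer that the schedule breaches the T6 window. It does not: day 150 is the first day of the window and day 180 its centre.

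**Conclusion.** The inconsistency is certain; its effect is unknown. Section 9.1 and Appendix E put T6 at about day 150 for intervention and about day 180 for control, a nominal gap of 30 days, against a common six-month target elsewhere. This is a modest, avoidable risk of arm-specific measurement timing, of minor severity. The 30-day figure rests on reading the labels as elapsed time from enrollment, as 9.1 says. It becomes a real gap only to the extent that sites used those labels as targets.

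Two stronger conclusions are tempting but unsupported. One is that the treatment estimate is biased: the documents give no actual test days and no rate of HbA1c change, so neither size nor direction can be derived. The other is that an earlier intervention test costs a definite amount of power. For example, if the 0.4 effect built up linearly over six months, a five-month test would show 0.4 × 5/6 = 0.33, with about 77% power at 300 per arm instead of 90%. The documents state no such accrual pattern, so that figure is not a finding.

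**What to change.** Reconcile 9.1 and Appendix E with 3.1.4, 3.6, 7.6 and 2.7 so that both arms share one elapsed-day T6 target within the existing 5 to 7 month window. The sponsor chooses the day.

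Report days from enrollment to the T6 HbA1c by arm, from the dates held in Access. The paper result form in Appendix AU carries a date but is shredded after entry, so confirm that Access keeps it. This table is useful even if T6 visits are already complete: it would either settle the question or make a timing difference visible.

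No further model is needed. Repeating the ANCOVA on days observed in both arms might exclude almost nobody and leave a difference in mean timing untouched.

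The cost is wording in two places, revised reminder dates and one descriptive table, with no extra visits or data. The small downside is that some T6 tests may no longer coincide with the final intervention box or the first control box, depending on the day chosen.

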9.4 Final Study/Early Discontinuation Evaluations

Participants should be actively followed through all study visits till the final visit, unless he or she withdraws informed consent.

It is important to note that if a study participant discontinues any part of the intervention but does NOT actively withdraw informed consent, he/she should still be followed to the end of the study. That is, participants in any component of the intervention (e.g. picking up food boxes, attending educational sessions) should still have HbA1c testing and complete follow-up survey as regularly scheduled.

10 Adverse Events and Safety Reporting

All adverse events should be reported to UCSF and [name] (FANO) **within 24 hours**. Study staff should complete an “Adverse Event” report (**Appendix AN**) for each incident that occurs, and enter the data into the MS Access database (if appropriate [involves a study participant] and when possible).

An adverse event can include study participants, or include study staff and food pantry clients that participate in any study activity (e.g. blood glucose screening event). An adverse event report should be completed for all events, with the one exception of low blood glucose screening results for pantry clients who do not report a history of diabetes. Food pantry clients with a blood glucose screening result < 70 mg/dL who do not report a history of diabetes do not require treatment by study staff, and the event does not need to be reported as an adverse event.

Adverse events which are reasonable to anticipate include:

1. Low blood glucose (hypoglycemia)
2. High blood glucose (hyperglycemia)
3. Reports of suicidality or homicidality
4. Reports of elder abuse or neglect
5. Reports of poor food quality
6. Study related injury

Each of these adverse events, along with steps on how to address, are discussed below.

